Effects of ambulation during the first stage of labour on maternal and neonatal

outcomes: A randomized controlled trial

Study Protocol with SAP

March 1, 2018

Effects of ambulation during first stage of labour on maternal and neonatal outcomes: A randomized controlled trial

Introduction

There is clear and important evidence that walking and upright positions in the first stage of labour reduces the duration of labour, the risk of caesarean birth, the need for epidural, (Lawrence, Lewis et al. 2013). In addition, ambulation and upright position have not been found to be associated with increased intervention or negative effects on mothers' and babies' wellbeing (Lawrence, Lewis et al. 2013). Women, particularly who have low risk labour, are highly advised to follow upright positions, and encouraged and assisted to assume whatever positions they choose (Lawrence, Lewis et al. 2013; Ondeck 2014).

Research confirms that movement is a safe and healthy coping strategy for pain, and confining labouring women to bed increases pain and decreases women's satisfaction with their birth experience (Romano and Lothian 2008; Ondeck 2014). An experimental study was conducted in Mangalore to examine the effect of ambulation during the first stage of labour on the intensity of labour pain, length of the first stage of labour, and use of analgesia, the study comprised of 40 primigravid mothers and they were grouped as experimental and control through randomization, experimental group received ambulation, the other group did not. Pain was assessed through Visual Analog Pain Scale and observational checklist was used to assess the outcome of labour there was a significant difference in duration of first stage of labour between the experimental and control group but no significant difference in overall outcome of labour. The mean pain

score for experimental group was (6.8) which was less than the main pain score of control group. The findings of the study revealed that ambulation was effective to reduce the intensity of labour pain among primigravid mothers (Savitha, Nayak et al. 2013).

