The setting for this study will be the maternity ward at Al-Karak hospital, the main governmental and teaching hospital in the southern region of Jordan. In 2016 2,808 births occurred in this hospital, 59% were caesarean births (Ministry of Health 2017). In this hospital, the woman usually labours in 26- bed ward with restrictions on movement. This is consistent practice nationally. Certified midwives, resident physicians, and obstetricians provide care. Midwives in this hospital work with uncomplicated labours and help obstetricians with complicated cases.

Sample and sampling

We will recruit consecutive eligible women interested in participating in the study, for a period of one year. All primiparous women with uncomplicated singleton pregnancies between 37 and 41 weeks gestation, cephalic, with cervical dilatation 3 to 5cm who come to give birth at Al-Karak hospital, between the 1st of January and the 30th of December 2018 will be approached for participation.

Sample size

The sample size was calculated using the G power version 3.1. Based on difference between two independent groups, alpha= 0.05, median effect size 0.3, power =95%, sample size required for each group is 88 women. To overcome attrition, 25% of the calculated sample will be added, the final sample size will be 110 women in each group.

Data collection process

Data will be collected using structured tool developed by the researchers based on literature review of research related to the current topic (appendix 1). The tool composed of section collecting the socio-demographic data and another section collecting maternal and neonatal outcomes. The research tool was reviewed by a panel (n=3) of experts in maternity health field. Before starting the study, the final version of the tool will be tested in a pilot study to evaluate its feasibility, clarity, and reliability. Assistant researcher (midwife) will complete the first section of the tool, which related to socio-demographic data, and will allocate participants to control and intervention group according to the randomization list.

The principal researcher will be kept blind for those participants who are in the intervention and control groups. Completing the second part of the study tool, which is related to maternal and infant health outcomes, will be in maternal ward and by the primary investigators 24 to 48 hours after birth.

Outcomes Measurement

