The study outcomes have two main aspects; related to maternal outcomes and neonatal outcomes. The maternal outcomes will include 1. Duration of the first stage of labour (defined as the time from the onset of regular contractions to the time of full cervical dilatation of 10 cm as documented by the midwife) 2. Intensity of labour pain (measured by the Visual Analogue pain Scale rating from 0 to 10 in which the woman registers the pain perception, considering 0 no pain and 10 the worst pain imaginable.) 3. Use of analgesics (defined as used or not used), 3. Mode of birth (defined as normal, vacuum extraction, forceps delivery, or cesarean section) 4. Woman satisfaction with the birth experience (measured by research-based birth satisfaction and dissatisfaction items from literature. Women will respond on a five-point Likert scale with agreements with the statement).

The new neonatal outcomes will include: 1. Apgar scores at 5 minutes

Data analysis

Data will be analysed using SPSS version 22. Descriptive statistics will be used to describe the sample characteristic. According to the level of measurement, independent *t*-test, and ANOVA will be used to examine the differences between study groups (intervention and control) based on baseline socio-demographic date and health

outcomes. Statistical assumptions will be checked and ensured, and results will be considered significant if P values were < 0.05.

Ethical consideration

Approval to conduct the study will be obtained from the ethics committee at faculty of nursing / Mutah University and the Ministry of Health (MOH). Women will be informed about the study and verbal and written consent for agreement will be obtained from each woman (appendix 2). Women will be assured that participation is voluntary and they have the right to withdraw from the study at any time without giving any reason. Women will be assured that their information will not be recognized in any products of this research.

References

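### Only tests of means are named for the health outcomes, so four-category mode of birth has no suitable test; taken literally, the result depends on arbitrary codes and does not measure a change in caesarean rate

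*Combined protocol and SAP*

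**What the plan says.** Under Outcomes Measurement, one maternal outcome is "Mode of birth (defined as normal, vacuum extraction, forceps delivery, or cesarean section"). No numeric codes, order or caesarean yes/no endpoint are given. Another is binary: "Use of analgesics (defined as used or not used").

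Under Data analysis, the comparison of arms on baseline data and outcomes begins "According to the level of measurement, independent *t*-test" and continues "and ANOVA will be used to examine the differences between study groups (intervention and control) based on baseline socio-demographic date and health" outcomes. The next sentence adds "Statistical assumptions will be checked and ensured" and sets significance at P < 0.05. No chi-square, Fisher or logistic method is named, and no fallback if an assumption fails. Descriptive statistics are assigned only to the sample characteristics.

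Two other places show why this outcome matters. The Introduction says that walking and upright positions in the first stage "reduces the duration of labour, the risk of caesarean birth, the need for epidural". The Setting section reports "In 2016 2,808 births occurred in this hospital, 59% were caesarean births".

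**The concern.** A mean needs numbers with meaningful spacing. Normal, vacuum, forceps and caesarean have none, so a t-test or ANOVA on this outcome needs codes that the plan does not give and the analyst would have to choose. Two things follow. The p-value can change with the numbering while the data stay the same. The estimate is a difference in average code, which cannot be translated into caesareans avoided. Caesarean birth is one of the outcomes that the Introduction expects ambulation to improve, at a hospital where more than half of births were caesarean, so an uninterpretable estimate here would leave one of the trial's practical questions unanswered.

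**Working it through.** **Inputs.** From the documents: the named tests, the four categories, alpha 0.05, and 110 women per arm (Sample size section: 88 × 1.25 = 110). The plan gives no figure for mode of birth, so there is none to reproduce. All tables below are assumptions, in the order normal/vacuum/forceps/caesarean. The control table 40/4/1/65 has 65/110 = 59% caesarean, matching the hospital figure. That figure covers all births, not only the low-risk primiparous women eligible here. The documents give no instrumental birth rate.

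**1. ANOVA is no alternative.** With two arms, F = t². In the first table below, t = -1.710 and F = 2.924, both with p = 0.0887.

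**2. Dependence on codes.** Control 40/4/1/65, intervention 45/13/4/48; t = difference in means / (pooled SD × √(2/110)), 218 df.
- Codes 1, 2, 3, 4 in the listed order: means 311/110 = 2.827 and 275/110 = 2.500; difference -0.327; pooled SD 1.419; standard error 0.191; t = -1.710; p = 0.089.
- Vacuum and forceps codes swapped (1, 3, 2, 4): means 314/110 = 2.855 and 284/110 = 2.582; difference -0.273; standard error 0.191; t = -1.429; p = 0.154.
- All 24 assignments of codes 1 to 4: 12 distinct p-values from 0.003 to 0.84, of which 4 are below 0.05. This range includes orders that nobody would be likely to choose.

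The caesarean comparison for the same women, 65 vs 48, does not depend on any code: chi-square p = 0.022; risk difference -15.5 points (95% CI -28.5 to -2.4); risk ratio 0.74 (0.57 to 0.96).

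**3. The mean-code difference is not a caesarean difference.** With codes 1 to 4, the difference in mean code = (change in vacuum + 2 × change in forceps + 3 × change in caesarean)/110, with changes as counts.
- 45/13/4/48: (9 + 2×3 - 3×17)/110 = -36/110 = -0.327. Caesarean change: -17/110 = -15.5 points.
- 52/4/1/53: (0 + 0 - 3×12)/110 = -36/110 = -0.327. Caesarean change: -12/110 = -10.9 points (chi-square p = 0.105).

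The reported estimate is the same for two different effects on caesarean birth.

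**4. Power.** Simulation with 100,000 runs per row, 110 per arm and alpha 0.05. The control distributions differ between rows, as shown.

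| Control (%) | Intervention (%) | t-test, codes 1-4 | Caesarean chi-square |
|---|---|---|---|
| 35/4/2/59 | 50/4/2/44 | 63% | 61% |
| 36/4/1/59 | 47/7/2/44 | 54% | 61% |
| 36/4/1/59 | 41/12/3/44 | 41% | 61% |
| 65/4/1/30 | 80/4/1/15 | 77% | 77% |
| 62/6/2/30 | 73/9/3/15 | 67% | 77% |
| 62/6/2/30 | 67/13/5/15 | 48% | 77% |

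Power is essentially equal when instrumental births are stable, and lower when they rise as caesareans fall. If only 88 per arm remain, the first row becomes about 54% and 53%, so absolute power falls but the comparison does not change.

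**5. Analgesic use.** For an assumed 55 vs 40 users of 110, the t-test on 0/1 codes gives p = 0.0414 and the chi-square 0.0412. The mean difference is the difference in proportions, -0.136.

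**The case against.** The strongest reply is that the plan never says mode of birth will be coded and averaged. Its sentence opens with "According to the level of measurement", assumptions are to be checked, and averaging nominal codes would break both commitments. On that reading the authors meant a chi-square and did not write it down. This has force: a reader might infer that the plan commits to a wrong method, and the documents do not establish that. What remains is that the opening phrase introduces a list containing only tests of means, and that neither sentence names a categorical test. The generous reading also leaves the contrast open, and the choice matters. For an assumed 57/4/1/48 against 40/4/1/65, caesarean versus vaginal gives p = 0.022, while the four-category exact test gives 0.090.

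Three further limits stand.
- A reader might hold it against the t-test that its p-value moves when the caesarean counts are fixed and the vaginal births split differently. That is not specific to averaging codes. Against the same control, the four-category exact test gives 0.021 for 45/13/4/48 and 0.090 for 57/4/1/48, both with 48 caesareans.
- A reader might infer a general loss of power. That needs instrumental births to rise as caesareans fall, which the documents neither predict nor exclude.
- With normal and caesarean at opposite ends of the scale, the two p-values for the main table, 0.089 and 0.154, are both above 0.05. With no instrumental births at all, p would not depend on the codes; only the size of the mean difference would.

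**Conclusion.** The point holds, for mode of birth only. On the literal reading the named method is unsuitable; on the generous reading the test and the contrast are unnamed. The specific harms of averaging codes are a p-value that changes with the numbering and a mean difference that cannot be reported as a change in caesarean rate. Their size rests on assumed tables, because the instrumental birth rate and the caesarean rate among eligible women are not in the documents. Loss of power is conditional and is not the main argument. The finding does not extend to analgesic use, where the t-test already compares proportions, and it asks nothing of the satisfaction or Apgar analyses. Since the wording leaves room for a correct analysis and no data are at risk, this should be fixed before analysis but does not undermine the trial.

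**What to change.** Keep the t-test for continuous outcomes and add to Data analysis:

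> *Mode of birth will be compared as caesarean versus vaginal birth by risk difference and risk ratio with 95% CI and a chi-square test (Fisher exact if any expected count is below 5); the four categories will be tabulated by arm, with a Fisher-Freeman-Halton exact test as supporting analysis.*

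The supporting test is exact because small expected counts are likely: in the six simulated scenarios, at least one four-category expected count was below 5 in 76% to 100% of runs. Another categorical contrast would serve equally well if it is named before the data are analysed. Reporting analgesic use in the same form is optional, not a correction.

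The cost is one sentence of wording, with no new data, visits or change in sample size.

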In Jordan practices in maternity wards are not based on best evidence(Shaban, Hatamleh et al. 2011). The majority of health facilities restrict movement during labour, women were confined to bed in the lithotomy position and most of these facilities strap women in the delivery position, women have no choice to assume the position they prefer during labour and delivery (Khresheh, Homer et al. 2007; Sweidan, Mahfoud et al. 2008; Shaban, Hatamleh et al. 2011). The practice of restricting women's movement in labour is contrary to the statements and recommendations of professional organizations advocate for women to move about during the first stage of labour, as long as they remain low-risk (WHO 1996; Ondeck 2014).

Implementing evidence-based maternity care in developing countries with limited resources such as Jordan is particularly challenging, and requires commitment to applying the most up to date evidence to clinical decisions.

Purpose of the study

The purpose of this study is to begin investigation that could help provide a better quality of care during birth and improve maternity outcomes in one Jordanian hospital. The process was introducing an evidence-based practice of encouraging women to ambulate and assume the upright position during the first stage of labour and observing if results would suggest low cost modifications for the maternity health service environment, especially the labour ward. This is the first study that has attempted to implement and evaluate such an intervention in Jordan. To examine the effect of ambulation (walking) during first stage of labour on maternal and neonatal outcomes.

Methods

Design

A randomised controlled study will be conducted with primiparous women who come to give birth at Al- Karak Hospital in Jordan. In the intervention group women will be encouraged to ambulate and women in the control group will receive usual maternity care. Women will be subsequently randomised into the groups using a table of random numbers. "Ambulation during labour" here will refer to moving from place to place during the first stage of labour that reduces the amount of time a woman spends laying down during this stage (measured by recording the number of minutes spend on walking).

Setting

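### Outcomes are compared by unadjusted t-test or ANOVA and baseline data are tested between randomised arms, while cervical dilatation at entry, known before allocation, is used in no planned analysis; the gain from using it is small but almost free

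*Combined protocol and SAP*

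**What the plan says.** - **Analysis (Data analysis).** The between-group plan is one sentence: an independent t-test and "ANOVA will be used to examine the differences between study groups (intervention and control) based on baseline socio-demographic date" and health outcomes, at P < 0.05. The only other statement about baseline is "Descriptive statistics will be used to describe the sample characteristic". There is no ANCOVA, regression, covariate list or stratified analysis, and no rule for what follows if the arms differ at baseline.
- **Eligibility (Sample and sampling).** Women are "cephalic, with cervical dilatation 3 to 5cm who come to give birth at Al-Karak hospital". Dilatation must therefore be assessed before allocation.
- **Allocation (Design).** "Women will be subsequently randomised into the groups using a table of random numbers". No stratification is described, so the design does not balance dilatation either.
- **First-listed outcome (Outcomes Measurement).** First-stage duration is "defined as the time from the onset of regular contractions to the time of full cervical dilatation of 10 cm". The clock starts before entry to the trial.
- **Tool (Data collection process).** The first section is described as socio-demographic. The tool itself is appendix 1, which is not in the text.

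**The concern.** Entry dilatation lies on the same scale that ends the first stage: a woman admitted at 3, 4 or 5 cm has 7, 6 or 5 cm still to go. It is therefore an obvious candidate covariate, and it is already being assessed. If it is related to outcome, leaving it out makes the confidence interval wider than it need be, and part of any chance difference in entry dilatation is carried into the estimated effect.

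The plan instead tests baseline data between arms. Under proper randomisation any baseline difference is due to chance, so the null hypothesis is known to be true and the P value does not show whether an imbalance matters for the outcome. Such P values also invite covariates chosen after the fact, or a claim of comparability that they cannot support. The tests named cover socio-demographic data, so dilatation might not be examined at all.

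**Working it through.** **1. The plan's own figures.** Sample size states "alpha= 0.05, median effect size 0.3, power =95%, sample size required for each group is 88 women". An exact two-sample t calculation at d = 0.3, alpha 0.05 and 95% power needs 290 per group two-sided or 242 one-sided, so 88 is not reproduced. (d = 0.5 one-sided gives 88, but those inputs are not stated.) The attrition step, 88 × 1.25 = 110, is reproduced. Below I take d = 0.3, two-sided 0.05, with 88 and 110 per arm. Unadjusted power is then 50.8% and 60.1%.

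**2. How much entry dilatation could explain.** The documents give no figure, so these are assumptions: D = 3, 4 or 5 cm equally likely (variance 2/3, mean square of 10 − D = 36.67); lognormal progress rate with mean 1 cm/h and CV c = 0.3 to 0.6. Hours per cm, T, then has mean 1 + c² = 1.09 to 1.36 and the same CV.

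- *Time from entry to 10 cm* (not the planned outcome), (10 − D)T: R² = 1/(1 + 55c²), which is 1/5.95 = 17% at c = 0.3 and 1/20.8 = 5% at c = 0.6.
- *Duration as defined, pre-entry labour independent of D, SD 3 to 5 h:*
  - c = 0.3, SD 3: explained variance 1.09² × 2/3 = 0.79; total 1.09² × (0.667 + 3.30) + 9 = 13.71; R² = 5.8%.
  - c = 0.6, SD 5: 1.36² × 2/3 = 1.23; total 1.36² × (0.667 + 13.2) + 25 = 50.65; R² = 2.4%.
- *Duration as defined, pre-entry time proportional to D at the woman's own later rate:* DT + (10 − D)T = 10T, which does not involve D; R² = 0.
- *Duration as defined, pre-entry progress half as fast, at an independent rate:* R² = 1/(1 + 155c²), which is 1/14.95 = 6.7% at c = 0.3 and 1/56.8 = 1.8% at c = 0.6. Here the slope is positive (2 × mean T − mean T), opposite in sign to the independent case.

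For the planned outcome, R² is therefore about 0 to 6%, touching 7% at one extreme. Neither its size nor the sign of the slope can be taken from the documents.

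**3. Power after adjustment.** Effective d = 0.3/√(1 − R²); equivalent sample size = n/(1 − R²).

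| R² | Effective d | Power, 88 per arm | Power, 110 per arm |
|---|---|---|---|
| 0 | 0.300 | 50.8% | 60.1% |
| 3% | 0.305 | 52.0% | 61.4% |
| 4% | 0.306 | 52.4% | 61.8% |
| 6% | 0.309 | 53.2% | 62.7% |

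At R² = 6% the gain is 2.4 to 2.6 points, worth 1/0.94 = 1.064, or about 6% more women.

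**4. Chance imbalance.** With 110 per arm, the 95% limit for the difference in mean entry dilatation is 1.96 × √(2/110) = 0.264 SD. With SD √(2/3) = 0.816 cm that is 0.216 cm. At R² = 6% (r = 0.245), an imbalance of that size moves the unadjusted estimate by 0.245 × 0.264 = 0.065 outcome SD. The type I error conditional on it is P(Z > (1.96 − 0.480)/0.970) + P(Z < −(1.96 + 0.480)/0.970) = 0.064 + 0.006 = 6.9%. Averaged over randomisations it stays at 5%.

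**5. Baseline tests.** With k independent tests at 0.05, the chance of at least one P < 0.05 under perfect randomisation is 1 − 0.95^k: 23% for k = 5, 40% for k = 10. The documents do not give k.

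**The case against.** The strongest case against acting is that the gain may be nil. The planned outcome starts at the onset of contractions, and a woman admitted at 5 cm has already covered ground that a woman at 3 cm has not. In the proportional model above, entry dilatation says nothing about total duration. That model is also an assumption, but it stands as a possibility the documents cannot exclude.

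Four stronger readings are tempting, and the documents do not support them.

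- A reader might infer that adjustment is worth 5-20% more women, with power of 53-58% (88 per arm) or 62-68% (110). Those figures follow from R² of 5-17%, which belongs to time from entry to 10 cm.
- A reader might multiply 0.216 cm by 1.09 to 1.36 h per cm and set the resulting 0.24 to 0.29 h against the one-hour shortening cited in the Introduction. That slope also belongs to time from entry, and 0.216 cm is a 95% limit, not a typical imbalance.
- A reader might say that baseline is handled solely by significance tests. Descriptive statistics are also planned, although they adjust nothing.
- A reader might say that dilatation is missing from the form. Appendix 1 cannot be seen, so only its absence from the planned analyses can be shown.

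It could also be said that ANOVA leaves room for further factors. With two arms and no factor or covariate named, it is the t-test again. Finally, nothing in the documents gives the size of any gain for pain, satisfaction, analgesic use, mode of birth or Apgar score.

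**Conclusion.** The point holds as a modest one about efficiency and good practice. No outcome comparison is adjusted, a baseline value known for every woman is unused, and baseline data are tested between arms to no useful end. A reader might infer that the planned comparison is biased or invalid. It is not: under randomisation the unadjusted difference is unbiased and its overall type I error is correct.

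For duration as defined, the gain at d = 0.3 lies between nothing and about 2 to 3 power points, resting on the assumed R² of about 0 to 6% and the progress model above. The case for acting rests on the low cost and on fixing the covariate in advance, not on a large gain. The case for dropping baseline P values does not depend on R² at all.

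**What to change.** - Make sure dilatation at entry (cm) is recorded as an analysis variable, adding the field to the tool if it is not already there.
- In Data analysis, prespecify a linear model (ANCOVA) of first-stage duration on arm plus entry dilatation as the main comparison, reporting the adjusted mean difference with its 95% CI.
- Where other outcomes are to be adjusted, say so in advance and use a model suited to the outcome, for example logistic regression for analgesic use.
- Replace the between-arm significance tests on baseline variables with a descriptive table by arm.

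**Cost.** At most one field on the form and a few sentences of plan wording. SPSS fits the model, and no extra women or visits are needed. The downside is one degree of freedom (174 to 173 with 88 per arm), which leaves power at 50.8% if the correlation is zero, so there may be little gain. None of this closes the gap between 88 per group and the 290 that the stated inputs require; the sample size needs separate attention.

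### None of the six outcomes is named as primary and each is judged at P < 0.05; the effect size of 0.3 and 95% power are tied to no outcome and, read as a standardised mean difference, do not give 88 per group

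*Combined protocol and SAP*

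**What the plan says.** The Outcomes Measurement section introduces the outcomes by type only: "The study outcomes have two main aspects; related to maternal outcomes and neonatal outcomes". Five are maternal: first-stage duration, pain on a 0–10 visual analogue scale, analgesic use (yes/no), mode of birth (four categories) and birth satisfaction (Likert items). The numbering uses 3 twice, so the list appears to end at 4. One is neonatal, the 5-minute Apgar score. None is labelled primary, main or secondary.

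The Data analysis section names the independent t-test and ANOVA; "ANOVA will be used to examine the differences between study groups (intervention and control") on baseline variables and health outcomes alike. Its only decision rule is "results will be considered significant if P values were < 0.05". It gives no adjustment, hierarchy or testing order.

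The Sample size section reads: "Based on difference between two independent groups, alpha= 0.05, median effect size 0.3, power =95%, sample size required for each group is 88 women". After a 25% addition for attrition, "the final sample size will be 110 women in each group". It names no outcome, effect-size index, standard deviation, event rate or sidedness.

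**The concern.** With no primary outcome, nothing in the plan stops the most favourable of six results from becoming the trial's message once the data are in. The 0.05 is then an error rate for each test, not for the main conclusion.

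The sample size section could have settled the matter by showing which outcome the trial was sized for. It names none, and its figures do not allow one to be inferred. A reader therefore cannot say what the 95% power refers to. If the target really is a standardised difference of 0.3, power is well below 95%, and a non-significant result would be hard to interpret.

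**Working it through.** **Inputs.** From Sample size: alpha 0.05, effect size 0.3, power 95%, 88 per group, 25% added, 110 per group. From Outcomes Measurement: six outcomes. From Data analysis: P < 0.05. Assumed: the effect-size index, the sidedness and the correlation between outcomes.

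**1. The plan's own figures.** 88 × 1.25 = 110, so the attrition step reproduces. A loss of 20% from 110 leaves 110 × 0.80 = 88, so 88 and 110 are the two sizes at which to state power.

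The 88 does not reproduce from 0.3. For two means, the normal approximation is n per group = 2(z₁ + z₂)²/d², where z₁ is the critical value and z₂ = 1.645 for 95% power.
- d = 0.3, two-sided: 2(1.960 + 1.645)²/0.09 ≈ 289; exact noncentral t gives **290**.
- d = 0.3, one-sided: 2(1.645 + 1.645)²/0.09 ≈ 241; exact **242**.

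**2. What does give 88.**
- d = 0.5, one-sided: 2(1.645 + 1.645)²/0.25 ≈ 87; exact **88** (power 95.1%).
- d = 0.5, two-sided: exact 105.

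**3. Other readings of 0.3 (per group, 95% power).**

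| Reading | n per group |
|---|---|
| Cohen's f, two-group ANOVA (equivalent to d = 0.6) | 74 |
| Chi-square w, 1 df | 73 |
| Chi-square w, 2 df | 86 |
| Chi-square w, 3 df | 96 |

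The nearest miss is w with 2 df: 172 in total, 86 per group. But no chi-square test is planned. Between two arms, analgesic use has 1 df and mode of birth 3 df, and no listed outcome has 2.

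**4. Power at d = 0.3.** The noncentrality is 0.3 × √(n/2).
- 88 per group: 0.3 × √44 = 1.990. Two-sided, Φ(1.990 − 1.960) = 0.512; exact **0.508**. One-sided, exact **0.632**.
- 110 per group: 0.3 × √55 = 2.225. Two-sided, Φ(2.225 − 1.960) = 0.604; exact **0.601**. One-sided, exact **0.717**.

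Turned round, a two-sided t-test reaches 95% power at d = 0.546 with 88 per group and d = 0.488 with 110.

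**5. Six tests at 0.05, all nulls true, one test each.**
- Independent: 1 − 0.95⁶ = **0.265**. Upper bound under any dependence: 6 × 0.05 = 0.30.
- Equicorrelated normal statistics, two-sided cut-off 1.96, 2,000,000 simulated draws: **0.207** at correlation 0.5 and **0.139** at 0.8.
- Six is a minimum count. If satisfaction were tested as two items instead of one score, there would be seven tests and, if independent, 1 − 0.95⁷ = 0.302.

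**The case against.** **The study is exploratory.** The Purpose section says "The purpose of this study is to begin investigation", and nowhere does the plan say that one significant result establishes benefit. This stands, and it limits the error-rate argument. A reader might infer that the trial has a 26% false-positive rate. The documents do not support that: the figure needs all six nulls true, one test each, and any significant result taken as the conclusion. It also treats all six as two-sided normal tests, although one outcome is binary and one has four categories. It is an illustration. Even so, a plan that claims 95% power has to say for which outcome.

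**Duration is listed first.** List order is not a designation, and the sample size section does not mention duration.

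**The 0.3 may be another index.** ANOVA is planned, so f is possible; at f = 0.3, power with 88 per group would be about 98%. A reader might infer that the true power could lie anywhere from about 51% to 98%. That blurs the finding. The text describes a difference between two groups and names the t-test first, which points to d, and neither f nor w yields 88.

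**The calculation may have used d = 0.5, one-sided.** The match is exact, but that this was done is an inference; the text states 0.3 and no sidedness. For the same reason, the documents do not show that the trial is underpowered for its real target, because that target is not given.

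**The timing.** The document is dated March 1, 2018, and eligible women "between the 1st of January and the 30th of December 2018 will be approached for participation". A reader might infer that outcomes had already been compared. Nothing says so, and the principal researcher is to be blind to allocation.

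**Conclusion.** The concern holds in two linked parts. First, six outcomes share an unordered P < 0.05 rule with no primary outcome, so the main conclusion can be selected after the fact. That adjustment is absent is read from the plan's silence on it. The illustrative chance of at least one false significant result is 26% if independent, about 21% and 14% at assumed correlations of 0.5 and 0.8, and more if satisfaction is tested item by item.

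Second, the stated 0.3 and 95% belong to no outcome and do not produce 88 per group on the natural reading. That reading needs 290 two-sided or 242 one-sided. The planned sizes give 51% to 60% power two-sided and 63% to 72% one-sided. These power figures rest on taking 0.3 as a standardised mean difference, which the plan suggests but does not state.

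This should be corrected, but it does not invalidate the design.

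**What to change.** Issue a short dated amendment before any comparison of outcomes by allocated group. It should:

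- name one primary outcome, tested at two-sided 0.05, and rest the main conclusion on it;
- report the other five as secondary, with 95% confidence intervals;
- state the effect-size metric and sidedness, and restate the power that 88 and 110 per group give for the named outcome. For a two-sided t-test, 95% power needs d of about 0.55 at 88 or 0.49 at 110;
- record how many women were already enrolled and that no between-group comparison had been made.

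The last condition is worded around group comparison for a reason. The primary investigators record outcomes themselves within two days of each birth, and the recruitment window opens before the plan's date. A statement that no outcome data had been seen might therefore be untrue.

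No change to recruitment is needed. The cost is that five outcomes become supportive and the restated power may be below 95%. If the sponsor confirms that a standardised difference of 0.3 is the target and 95% power is required, recalculating the sample size is a separate and much larger decision (290 per group two-sided).
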